#### **1.4.6 Rationale for use of Blood and Tumor Tissue Biomarkers**

Previous ipilimumab studies explored in their main study design a variety of potential biomarkers in melanoma patients. Results from studies CA184004 and CA184007 suggested the possible biomarkers listed below for further research:

- An increase in peripheral-blood Absolute Lymphocyte Count (ALC) was associated with benefit (Best Overall Response of Complete Response, Partial Response, or prolonged Stable Disease (SD), i.e. SD lasting at least 24 weeks from first dose) and occurred in a dose-dependent fashion favoring 10 mg/kg ipilimumab. In addition to change in ALC over time, ALC value just prior to a third dose of ipilimumab also was associated with benefit.

We will also evaluate FOXP3 and IDO tumor tissue expression at baseline as predictive of clinical benefit, as well as flow cytometry of CD4 and CD8 T cells for Ki67, EOMES and ICOS, predictive markers that have been found to be associated with benefit using ipilimumab. Serum cytokine assays with a multiplex analysis for IL-6, IL-10 and gamma interferon will be conducted, as well as T cell intracellular staining for those cytokines and assessment of allo MLR reactivity as a marker of T cell integrity.

[figure not shown]
A mean increase in the percentage of activated (HLA-DR+), CD4+ and CD8+ T cells and central memory (CD45-RO and CCR9+) T-cells and a mean decrease in percent of naive CD4+ and CD8+ T-cells in Week 4 and Week 12 post-ipilimumab treatment samples has been observed in several studies. Based on these results, a biomarker plan is included in this trial which allows sample collection for biomarker analyses to determine the effects of PANOBINOSTAT on the immune-regulatory effects of ipilimumab treatment. Subjects will

be asked to give blood samples, serum and/or tumor tissue samples for predictive, pharmacodynamic and exploratory biomarker research.

[figure not shown]

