#### **4.3.4 Duration of Treatment**

Subjects may remain on study therapy until progressive disease as determined by immune-related response criteria (irRC), withdrawal due to toxicity, withdrawal of consent, or at the discretion of the investigator.

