**Table 5.12 During Treatment, Day 1 onward**

Study Cycle	Induction Cycle						Maintenance Cycle	End of Treatment	Follow-up	Notes
Cycle #	1				2		Each Cycle			
Day of Cycle 	1	5	22	35	1	22				
Safety Assessments										
Physical exam	X 		X		X	X	X	X	X	
Ophthalmology Exam	X									Baseline only
Vital Signs	X		X		X	X	X	X	X	
Weight	X		X		X	X	X	X	X	
PS	X 		X		X	X	X	X	X	
ECG	X 	X 			X		X	X		Triplicate 12-lead for Induction Cycle 1 Day 1 & Day 5; single 12-lead ECG otherwise
Chem Panel, CBC	X 		X		X	X	X	X	X	
PT/PTT	X 									
T4, TSH	X 		X		X	X	X			
Serum Preg	X 						X			
Urinalysis	X 				X		X			
SAE Monitoring	X		X		X	X	X	X	X	
Ipilimumab	X		X		X	X				
Panobinostat	X		X		X	X	X 			
Disease Assessment					X		X	X	X	
PD Blood	X		X		X	X	X	X		
Tumor bx				X 						

 All study visits may be scheduled +/- 3 days from planned visit date.

 These tests will not be repeated on Cycle 1 Day 1 of the initial treatment period if completed for screening less than 72 hours (3 days) before the first dose of the study drugs.

 Triplicate ECGs at least 5 minutes apart will be done pre-dose on C1 D1 & C1 D5.

 Biopsy to be done between Days 35 and 42.

 Panobinostat will continue to be administered thrice weekly during the maintenance cycles.

6. Patients will continue to be followed for PFS and OS.

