### 8.2.2 Efficacy Endpoints

#### 8.2.2.1 Efficacy Endpoints based on RECIST 1.1

The best overall response (BOR), computed for all treated subjects, is defined as the best response designation over the study as a whole, recorded between the dates of first dose until the last tumor assessment prior to subsequent therapy.

**Objective Response Rate (ORR)** is defined as the total number of subjects whose best response outcome is a complete response (CR) or partial response (PR) divided by the total number of evaluable subjects.

**Disease Control Rate (DCR)** is defined as the total number of subjects whose best response outcome is a complete response (CR) or partial response (PR), or stable disease divided by the total number of evaluable subjects.

**Prolonged Disease Control Rate (PDCR)** is defined as the total number of subjects whose best response outcome is a complete response (CR) or partial response (PR), or stable disease lasting at least 12 weeks, divided by the total number of evaluable subjects.

**Progression Free Survival (PFS):** is defined for each subject as the time from first dosing to the first observation of disease progression or death due to any cause. If a subject has not progressed or died at the time of analysis, PFS will be censored on the date of the last disease assessment. Subjects who do not have any tumor assessment on treatment will be censored on the day of the first dose.

**Duration of Overall Response:** will be computed for all subjects whose best response is either a PR or CR and is calculated from the time the measurement criteria are met for PR or CR, whichever is recorded first, until the date of documented progressive disease or death.

**Duration of Disease Control:** will be computed for the subjects who had BOR outcome of CR, PR, or Stable Disease and is calculated from the beginning of treatment until the time of documented disease progression.

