**8.2.2.2 Efficacy Endpoints based on Immune Related Criteria (irCR)**

**Immune Related Best Overall Response (irBOR)** is the best irRC designation over the study as a whole, recorded between the date of first dose until the last tumor assessment prior to subsequent therapy (except for local palliative radiotherapy for painful bone lesions) for the individual subject in the study. irCR or irPR determinations included in the irBOR assessment must be confirmed by a second (confirmatory) evaluation meeting the criteria for response and performed no less than 4 weeks after the criteria for response are first met.

**Immune-related Response Rate (irRR)** is defined as the proportion of response evaluable subjects whose irBOR outcome is irPR, irCR.

**Immune-related Disease Control Rate (irDCR)** is defined as the proportion of the response evaluable subjects whose irBOR outcome is irPR, irCR, or irSD.

**Immune-related Prolonged Disease Control Rate (irPDCR)** is defined as the proportion of the response evaluable subjects whose irBOR outcome is irPR, irCR, or irSD, with stable disease lasting at least 12 weeks.

**Immune-related Progression-Free Survival (irPFS)** is defined as the time between the first dosing date and the date of irPD or death, whichever occurs first. For subjects with no recorded post-baseline tumor assessment, irPFS will be censored at the day of first dose. A subject who dies without reported irPD will be considered to have progressed on the date of death. For those who remain alive and have no irPD, irPFS will be censored on the date of last evaluable tumor assessment. Subjects who do not have any tumor assessment on treatment will be censored on the day of the first dose.

**Duration of Immune Related Overall Response:** will be computed for all subjects whose irBOR outcome is either an irPR or irCR and is calculated from the time the measurement criteria are met for irPR or irCR, whichever is recorded first, until the date of documented progressive disease or death by irRC.

**Duration of Immune Related Disease Control:** will be computed for the subjects who had irBOR outcome of irCR, irPR, or ir Stable Disease and is calculated from the beginning of treatment until the time of documented disease progression by irRC.

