### 8.3.4 Biomarker Analyses

Pharmacodynamic analyses will examine the patterns of change in ALC over time, and how these patterns might differ between treatment arms. Predictive analyses will examine potential relationships between ALC and measures of response such as PFS or irPFS. The mean rate of change in ALC over time and corresponding two-sided 95% CIs will be estimated using an extended linear model, fit by restricted maximum likelihood (REML). The model will have fixed effects of treatment and time since first dose. Predictive analyses will assess the relationship between PFS / irPFS and rate of change in ALC over time (ALC slope). Summary statistics for peripheral blood biomarkers of immunoregulatory activity such as, but not limited to T-cell subpopulation counts, serum cytokines, and their corresponding changes (or percent changes) from baseline will be tabulated by planned study day and dose in each arm, to assess pharmacodynamic effects. In addition, the time course of biomarker measures will be investigated graphically; if there is indication of meaningful pattern across time, further analysis (eg, by linear mixed models) may be performed to characterize the relationship. Possible associations between changes in biomarker measures of interest and panobinostat exposure will be explored graphically. Summary statistics for measures and changes from baseline of tumor-based markers including T-cell (CD4, CD8, CD45, FoxP3) and apoptosis markers (IDO and granzyme B) will be tabulated by study visit for each arm. Results from mRNA expression profiles pre- and on-treatment, in peripheral blood and fresh tumor biopsies and from T cell phenotype analysis on baseline samples will be tabulated, and possible associations with clinical outcome (e.g. tumor response) will be explored based on data availability. Associations between biomarkers and efficacy measures will be analyzed in all response-evaluable subjects. Methods such as, but not limited to, logistic regression will be used to explore possible associations between biomarker measures from peripheral blood or tumor markers and clinical outcome, e.g. tumor response, based on both RECIST 1.1 and irRC criteria.

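### The PFS/irPFS analysis on ALC slope in Section 8.3.4 states no ALC window or landmark, so the slope depends in part on how long the subject stayed progression-free

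*Combined protocol and SAP*

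**What the plan says.** Section 8.3.4 (Biomarker Analyses) sets out the ALC slope in two steps. First, "The mean rate of change in ALC over time and corresponding two-sided 95% CIs will be estimated using an extended linear model", fitted by REML, and "The model will have fixed effects of treatment and time since first dose". Second, "Predictive analyses will assess the relationship between PFS / irPFS and rate of change in ALC over time (ALC slope"). No upper limit on time, landmark, time-dependent covariate, joint model or minimum number of ALC values appears in the visible text. The model yields a mean rate of change, and how each subject's own slope is obtained is not stated. Associations with efficacy are to be examined in all response-evaluable subjects.

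The outcomes share the ALC model's time origin. PFS "is defined for each subject as the time from first dosing to the first observation of disease progression or death due to any cause" (Section 8.2.2.1), and irPFS "is defined as the time between the first dosing date and the date of irPD or death, whichever occurs first" (Section 8.2.2.2).

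ALC comes from the row "Chem Panel, CBC" of Table 5.12: days 1 and 22 of each induction cycle, each 84-day maintenance cycle, end of treatment and follow-up. Section 4.3.4 says what ends treatment: "Subjects may remain on study therapy until progressive disease as determined by immune-related response criteria (irRC"), or toxicity, withdrawal or investigator discretion.

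Section 1.4.6 also cites a fixed-time measure: "ALC value just prior to a third dose of ipilimumab also was associated with benefit". In this trial that is Cycle 2 Day 1 (study day 43), when blood is already drawn. Section 8.3.4 does not use it.

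**The concern.** A predictor of PFS should be known before the period over which PFS is counted. Here the slope is built from measurements taken during that period, and a subject who stays progression-free longer contributes more of them over a longer span. This has two consequences.

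- **Unequal windows on a curved path.** If ALC moves early and then flattens, a short window catches only the steep part and a long one averages it with the plateau. Subjects with identical ALC biology then get different slopes because they progressed at different times.
- **Unequal precision.** Even on a straight path, slopes from short follow-up are far noisier, so extreme values collect among early progressors.

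At stake is the reading of one biomarker. Section 1.4.6 reports that a rise in ALC went with benefit. The planned analysis could falsely contradict that or, if ALC falls and then levels off, falsely support it.

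**Working it through.** The plan gives no sample size, test or significance level for this analysis, so there is no figure of its own to reproduce. Two checks were made.

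**1. Least squares on the protocol's CBC days**

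Inputs: study days 1, 22, 43 and 64 (Table 5.12), then day 85 and every 84 days, reading the maintenance entry as day 1 of each cycle. End-of-treatment and follow-up samples are left out. Assumed curve: ALC changes linearly to day 64 and is then flat, f(d) = min(d − 1, 63)/63.

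Formulas: slope b = Sxy/Sxx, with Sxx = Σ(d − d̄)² and Sxy = Σ(d − d̄)f(d). The early slope is 1/63 per day, so the relative slope is 63·Sxy/Sxx. The standard error is σ/√Sxx, so precision relative to week 6 is √(Sxx/882).

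| Follow-up to | CBCs | Sxx | Sxy | Relative slope | SE smaller by a factor of |
|---|---|---|---|---|---|
| Week 6 | 3 | 882 | 14 | 100% | 1 |
| Week 12 | 5 | 4,410 | 56 | 80% | 2.2 |
| Week 24 | 6 | 17,640 | 98 | 35% | 4.5 |
| Week 48 | 8 | 101,209.5 | 213.5 | 13% | 10.7 |

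For example, at week 24: 63 × 98/17,640 = 0.35 and √(17,640/882) = 4.5. The precision column needs only the schedule. The slope column also needs the assumed plateau.

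**2. Simulation with ALC unrelated to PFS**

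Inputs from the documents: 36 subjects (Section 3.1), scans at weeks 6 and 12 and then every 12 weeks (Section 5.4), and the CBC days above. Assumptions not in the documents: exponential PFS, with median 3 or 6 months or matched to the six-month progression-free proportions of 11% and 34% in Section 1.4.2.3; within-subject SD of 0.30 to 0.35; in the Cox runs with stated inputs, a between-subject SD of ALC change of 0.2; a mean change of ±0.3 or +0.6 (×10⁹/L) reached by about week 9; and per-subject least-squares slopes over all data up to progression. Rejection is at two-sided 5%.

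| ALC path, n = 36 | Spearman | Cox |
|---|---|---|
| Linear | 6–8% | 15–22%, split about evenly in direction |
| Plateau, +0.3 | 23–46% | 17–76% |
| Plateau, −0.3 | not run | 60–75%, opposite sign |
| Plateau, +0.6 | not quoted for n = 36 alone | 95–98% |

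The ranges cover different PFS and variance assumptions. With a rise, the false finding is that a steeper rise goes with shorter PFS.

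Variants at n = 36:

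- Keeping ALC values for 12 weeks after RECIST progression did not remove the effect (80% plateau, 10% linear).
- Shrunken random slopes reduced it (18% plateau, 5% linear). This rests on 60 runs with many convergence warnings. The simulation error on 18% is about √(0.18 × 0.82/60) = 5 points, so the result is only indicative.
- Giving every subject the same long ALC window regardless of PFS brought rejection back to 5.6%.
- A day-43 landmark gave 4.8–6.0%.

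**Subjects lost at a week-6 landmark**

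- Six-month rate 11%: 0.11^(6/26) = 0.60, so 36 × 0.40 = 14.4 lost.
- Six-month rate 34%: 0.34^(6/26) = 0.78, so 36 × 0.22 = 7.9 lost.
- Median PFS of 3 to 6 months: about 26 to 31 remain, so 5 to 10 are lost.

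Overall, roughly 5 to 15 of 36 are lost.

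**The case against.** The strongest objection is that the window may be defined where it cannot be read. The contents list Section 5.5.1 (Absolute Lymphocyte Count), which is redacted, and Section 8.2.3 (Biomarker Endpoints), which is not visible. This stands as a limit: using all follow-up is the default reading of Section 8.3.4, not something the text states. If either section sets a window, Section 8.3.4 should cite it.

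A reader might infer that PFS itself fixes the length of each slope. The documents do not support that. Treatment stops on irRC progression or for other reasons, reported PFS uses RECIST 1.1, and CBCs are also taken at end of treatment and at a follow-up visit at least 90 days later. The link is close for irPFS and looser for RECIST PFS. The 12-week extension shows that loosening it does not remove the problem.

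The size also depends on assumptions. The plateau, the amount of change and the variances are not in the documents, and the 34% rate comes from ipilimumab 10 mg/kg, which is not used here. The simulated per-subject slopes are not the REML model named in the plan, although the plan does not say how that model would give a subject's slope. A linear path gives no directional bias.

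Finally, the analysis is modest in standing. ALC is one of many markers, relating biomarkers to activity is an exploratory objective, and the planned graphs of biomarker time courses could reveal a plateau. All of this stands and limits the importance of the point. A graph would not by itself correct the association.

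**Conclusion.** The point holds as a cheap improvement. On the visible text, predictor and outcome are measured over the same interval, and the span and precision of the slope grow with irPFS and, less tightly, with RECIST PFS. The schedule alone makes slopes up to 10.7 times more precise at week 48 than at week 6. A false or reversed association also needs ALC to change early and then level off, which is an assumption. Under it, null rejection at n = 36 with a 0.3 change ranges from about 17% to 76%, depending on the test, variances and PFS. Under a linear path it ranges from near nominal to about 20%, with no preferred direction.

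Two stronger readings are not supported. The bias need not favour a benefit, since its sign follows the direction of the early ALC change. Nor do the documents present ALC as the trial's main pharmacodynamic marker or tie any dose decision to this analysis, so MTD and safety conclusions are unaffected.

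**What to change.** In Section 8.3.4, define the predictor as each subject's ALC change estimated from the Day 1, Day 22 and Cycle 2 Day 1 samples only. Relate it to PFS and irPFS counted from Cycle 2 Day 1, among subjects still progression-free at that visit. Because the week-6 scan falls at about the same visit, state that progression on that scan counts as before the landmark. State how many ALC values a subject must have, and report how many subjects are excluded and why. If Section 5.5.1 or 8.2.3 already sets a window, cite it and align the start of PFS with it.

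The cost is wording only, with no new samples or visits. The analysis loses roughly 5 to 15 of 36 subjects under the assumed PFS rates. These are the early progressors, and a slope from three samples is noisy. A later landmark at day 85 also keeps the error rate near nominal (5.8–6.4%) but leaves only about 19 to 26 subjects.

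An acceptable alternative that keeps early progressors is a time-dependent ALC covariate or a joint longitudinal-survival model. A joint model should let the ALC path bend, and with at most 36 subjects its stability would need checking.

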## **9 STUDY MANAGEMENT**

### **9.1 Compliance with the Protocol and Protocol Revisions**

The study shall be conducted as described in this protocol. The investigator should not implement any deviation or change to the protocol without prior review and documented approval/favorable opinion from the IRB/IEC of an amendment. Any significant deviation must be documented in the CRF. If a deviation or change to a protocol is implemented to eliminate an immediate hazard(s) prior to obtaining IRB/IEC approval/favorable opinion, as soon as possible the deviation or change will be submitted to: IRB/IEC for review and approval/favorable opinion. Documentation of approval signed by the chairperson or designee of the IRB(s)/IEC(s) will be sent to Novartis. If an amendment substantially alters the study design or increases the potential risk to the subject: (1) the consent form must be revised and submitted to the IRB(s)/IEC(s) for review and approval/favorable opinion; (2) the revised form must be used to obtain consent from subjects currently enrolled in the study if they are affected by the amendment; and (3) the new form must be used to obtain consent from new subjects prior to enrollment. If the revision is an administrative letter, investigators must inform their IRB(s)/IEC(s).

### **9.2 Monitoring**

This study will be monitored internally by the Moffitt Cancer Center Monitoring Core.

Representatives of Novartis will be allowed to visit the study site periodically to assess the data quality and study integrity. On site they will review study records and directly compare them with source documents, discuss the conduct of the study with the investigator, and verify that the facilities remain acceptable. The investigator must notify Novartis promptly of any inspections scheduled by regulatory authorities, and promptly forward copies of inspection reports to Novartis.

## **9.3 Records**

### **9.3.1 Records Retention**

The investigator must retain all study records and source documents for the maximum period required by applicable regulations and guidelines, or institution procedures, or for the period specified by the sponsor, whichever is longer. The investigator must contact Novartis prior to destroying any records associated with the study. If the investigator withdraws from the study (eg, relocation, retirement), the records shall be transferred to a mutually agreed upon designee (eg, another investigator, IRB).

### **9.3.2 Study Drug Records**

It is the responsibility of the investigator to ensure that a current disposition record of investigational product (panobinostat supplied by Novartis) is maintained at the study site. Records or logs must comply with applicable regulations and guidelines and should include:

- amount received and placed in storage area
- amount currently in storage area
- label ID number or batch number
- amount dispensed to and returned by each subject, including unique subject identifiers
- amount transferred to another area/site for dispensing or storage • non-study disposition (eg, lost, wasted) • amount destroyed at study site, if applicable • amount returned to the sponsor
- retain samples for bioavailability/bioequivalence, if applicable • dates and initials of person responsible for Investigational Product (IP) dispensing/accountability, as per the Delegation of Authority Form.

The sponsor will provide forms to facilitate inventory control if the investigational site does not have an established system that meets these requirements.

### **9.3.3 Case Report Forms**

An investigator is required to prepare and maintain adequate and accurate case histories designed to record all observations and other data pertinent to the investigation on each individual treated or entered as a control in the investigation. Data reported on the CRF that are derived from source documents must be consistent with the source documents or the discrepancies must be explained. The confidentiality of records that could identify subjects must be protected, respecting the privacy and confidentiality rules in accordance with the applicable regulatory requirement(s). The investigator will maintain a signature sheet to document signatures and initials of all persons authorized to make entries and/or corrections on CRFs. The completed CRF, including any paper SAE/pregnancy CRFs, must be promptly reviewed, signed, and dated by a qualified physician who is an investigator or sub-investigator.

